### 6.2 Justification of the investigation design and outcome measures

In order to answer the proposed hypothesis, that there will be a significant improvement in aided thresholds with the Sentio 1 compared to unaided, a prospective, within subject controlled clinical investigation will be performed.

The single-arm design and the primary endpoint evaluation of performance reflects a typical clinical investigation design in the field.

Thus, this investigation will be a pre-market, confirmatory investigation with the purpose to confirm the performance of the Sentio 1 sound processor on users previously implanted with the I1 implant. The investigation includes four visits and three field trial periods. On the first visit the subjects will be fitted with the Sentio 1 according to the audiological manual [D]. The first field trial period will allow the subjects to get adapted to the sound in the Sentio 1. After one month (visit window +4 weeks) a follow up visit is conducted to evaluate the Sentio 1 sound processor. The investigation design in regards of fitting of and adaptation time to the Sentio 1 corresponds to standard clinical practice. A field period is conducted after the second and third visit with the purpose to monitor the safety of the Sentio 1 to assure long term safety data. The follow

	Title Clinical Investigation Plan BC114	Document no Doc-00117705	Revision 4	Page 13(39)
---	---	------------------------------------	----------------------	-----------------------

up visit after one and two years will be conducted as a physical or remote meeting depending on subjects' preference.

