### 8.2 Secondary Objective(s)

Secondary objective(s)	Corresponding secondary endpoint/outcome variable(s)	Section
B. To assess the improvement of hearing with the Sentio1.	1. Functional gain with Sentio 1, i.e., the difference in dB between unaided and aided sound field thresholds, for all measured frequencies.	9.5.3.2.1
C. To assess self-reported performance with the Sentio 1 compared to previous sound processor after at least one month field usage of the Sentio 1	1. Average SSQ12 scores with Sentio 1 for each question, sub-scales and in total. 2. Average SSQ12 scores with current sound processor for each question, sub-scales and in total.	9.5.4.1

	3. Difference in SSQ12 scores between Sentio 1 and current sound processor for each question, subscales and in total.	
D. To assess the preference of sound processor.	1. Percentage (%) of subjects who prefer the Sentio 1 over current sound processor	9.5.4.2
E. To assess the degree to which Sentio 1 compensates for the BC hearing loss	1. Effective gain defined as the difference in dB between aided sound field thresholds with Sentio 1 and unmasked BC thresholds on the aided ear(s). The effective gain is calculated for all measured frequencies. 2. Effective gain with Sentio 1, see definition above, calculated in average for frequencies 500, 1000, 2000 and 4000 Hz (PTA4).	9.5.3.2.2
F. To assess the difference between BC in-situ thresholds measured with Sentio 1 and conventional unmasked BC audiometry.	1. Difference in dB between Sentio 1 BC in situ thresholds and BC thresholds measured with conventional unmasked BC audiometry for the frequencies 500, 1000, 2000, 3000 and 4000 Hz	9.5.3.1 9.5.1
G. Assess safety with the Sentio 1 sound processor	1. Tabulation of AEs occurred throughout the investigation and percentage of individuals with reported AEs.	18

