## 9 DESIGN OF THE CLINICAL INVESTIGATION

### 9.1 General

The investigation is prospective, single-center, comparative investigation with within-subject control design. It is estimated that 12-14 subjects previously implanted with the I1 implant will be fitted with Oticon Medical Sentio 1 sound processor.

The investigation includes two laboratory visits at the research unit at Chalmers tekniska högskola ([name]), with a field trial period between. Both visits will take between 2-3 hours including breaks. At the first visit the subject's current device is evaluated and Sentio 1 is fitted according to the audiological manual [D]. Audiological measurements will be conducted. If needed, finetuning will be applied according to the subject's preference. Retention will be assessed and the magnet in the sound processor will be adjusted according to the investigator judgement and subject needs and preference. The subjects will wear the Sentio 1 in their daily life for 1 month (visit window +1 month). During

the field trial the subjects will fill out one questionnaire. At the second visit, any AE that occurred in the field trial will be evaluated. Audiological measurements will be conducted. If needed, finetuning will be applied according to the subject's preference. Retention will be assessed and the magnet in the sound processor will be adjusted according to the investigator judgement and subject needs and preference. A preference questionnaire will be filled out during the visit. A third and fourth visit are scheduled after one and two years respectively of using the device, with the main purpose to monitor safety using the device. Visit 3 can be conducted at Chalmers or at the Hearing clinic in Gothenburg or as a telephone visit. Visit 4 will take place at the Hearing clinic in Gothenburg.

Due to the nature of the end points (comparisons between aided and unaided, and Sentio 1 and current sound processor) there is no possibility to blind the investigation as the conditions are obvious for the subject.

Enrollment of subjects is expected to occur in the second half of 2022, after approvals from the Ethical Committee (EC) and Regulatory Authority (Läkemedelsverket, LMV). The investigation will be considered completed when the last subject has completed the last visit.

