#### 9.4.1 *Clinical Investigation visits*

##### 9.4.1.1 Visit 1 (screening/baseline visit)

Following procedures will be carried out during the first visit. The flow below is a suggested flow, based on convenience for subject and investigator the order may be changed. Information, informed consent and screening will always be carried out before any investigation related procedures are conducted.

- The subject is thoroughly informed about the investigation including all investigation related visits. Time will be given for consideration and answering any questions the subject might have.
- Consent form is signed.
- Screening according to inclusion and exclusion criteria.
- The subject's demographical data as well as their personal data and subjects' characteristics are registered.
- Audiometry is performed
- Fitting and adjustment of the Sentio 1 is performed
  - Including BC in-situ and feedback management measurement.
  - Strength of retention magnet is considered and potentially changed according to the subject's needs and preference.
  - Finetuning is considered and Sentio 1 is adjusted according to the subject's needs and preference.
- [REDACTED]
- Questionnaire for evaluation the subject's current hearing solution is filled out.
- Questionnaires for evaluation of the Sentio 1 is handed out and instructions to fill them out prior to next visit is given.
- AEs are assessed.

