##### 9.4.1.2 Visit 2 follow up (1 month)

Following procedures will be carried out at visit 2. The flow below is a suggested flow, based on convenience for subject and investigator the order may be changed.

- AEs are assessed.
- Questionnaires is handed in and checked for completeness.
- Aided and unaided sound field thresholds are performed.
- Preference questionnaire is filled out.
- Adjustment of the Sentio 1 is considered.
  - Strength of retention magnet is considered and potentially changed according to the subject's needs and preference.
  - Finetuning is considered and Sentio 1 is adjusted according to the subject's needs and preference.

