### 9.5.3.3 [REDACTED]

### 9.5.4 Patient Related Outcomes (PRO)

#### 9.5.4.1 Speech Spatial and Qualities of hearing scale (SSQ)

[figure not shown]
A reduced version of the Speech, Spatial and Qualities of Hearing Scale (SSQ) questionnaire [3], the SSQ12,

	Title Clinical Investigation Plan BC114	Document no Doc-00117705	Revision 4	Page 24(39)
---	---	------------------------------------	----------------------	-----------------------

will be used in this investigation. The SSQ12 was developed and validated by Noble, Jensen [4] and contains 12 questions that reflect the perceived performance in speech intelligibility, spatial abilities, and sound quality. Each item is scored from 0 to 10, with larger values always indicating greater ability. The SSQ12 will be assessed at visit 1 (own device) and at visit 2 (Sentio 1).

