#### **Missing data**

Handling of missing data will be described in the SAP. In order to minimize missing data, the importance of complete follow up data sets will be emphasized to investigators and investigation site staff, as will the importance of recruiting subjects who are motivated to undergo treatment and participate in the investigation. The investigation site is leading in the field of bone conduction devices, thus familiar with the outcomes of the treatment, and what level of treatment compliance that can be expected from patients considering undergoing treatment with a device. The sites will also have experience in conducting clinical investigations and recruiting investigation subjects. The patient information will give the subjects a clear understanding of the design of the investigation and the visit schedule. The latter has been carefully considered to mimic the standard practice of treatment with a bone conduction device, but also to be feasible in relation to the burden on the investigation subjects as a mitigation measure to avoid drop-outs and/or missing appointments. In addition, subjects will be given the opportunity to complete out PROs at the applicable site visits if they have forgotten to bring them or to complete them on beforehand.

Monitoring through the electronic data capturing system will be performed all through the investigation period. Early and close monitoring of the eCRFs will enable the Sponsor to take action and get back to site if missing data and/or deviations are found. The Sponsors representatives will be in close contact to site to give support and training for general quality assurance of the data captured in the investigation

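### The Sentio 1 SSQ12 goes home at fitting with no earliest completion day, so ratings may predate the month of use that objective C requires

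*Combined protocol and SAP*

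**What the plan says.** - **Objective.** Section 8.2 (and the synopsis) defines objective C as self-reported performance "after at least one month field usage of the Sentio 1". C1 is the Sentio 1 score, C2 the current-device score and C3 their difference.
- **Reason for the waiting period.** Section 6.2: "The first field trial period will allow the subjects to get adapted to the sound in the Sentio 1".
- **Nominal timing.** Section 9.5.4.1: "The SSQ12 will be assessed at visit 1 (own device) and at visit 2 (Sentio 1"). The flow chart in section 9.4 agrees, with Visit 2 at 1 month.
- **Procedure at fitting.** Section 9.4.1.1: "Questionnaires for evaluation of the Sentio 1 is handed out and instructions to fill them out prior to next visit is given".
- **Field period.** Section 9.1 says that during "the field trial the subjects will fill out one questionnaire". On its length: "The subjects will wear the Sentio 1 in their daily life for 1 month (visit window +1 month"). Section 6.2 gives the window as +4 weeks.
- **Procedure at Visit 2.** Section 9.4.1.2: "Questionnaires is handed in and checked for completeness".
- **Fallback.** Section 12, under Missing data: "subjects will be given the opportunity to complete out PROs at the applicable site visits if they have forgotten to bring them", or have not completed them beforehand.

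**The concern.** The objective fixes a minimum exposure of one month, but the visit procedures attach no minimum exposure to the form that measures it. The current device is rated at Visit 1 by someone who already uses it. The Sentio 1 may be rated at any point between fitting and Visit 2. Any timing effect therefore enters only one side of the paired difference C3. Early ratings could be too high because the device is new, or too low because the sound is unfamiliar. In either case C1 and C3 would not describe the adapted state named in the objective. The point deserves attention because SSQ12 is the only secondary endpoint that section 11.1 uses to support the sample size.

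**Working it through.** **1. Which form goes home.** Section 9.4.1.1 does not name it. The PRO block of the flow chart lists two instruments, SSQ12 and preference. Sections 9.1 and 9.4.1.2 have the preference form filled in during Visit 2. That leaves the SSQ12, which fits the single field-trial questionnaire of section 9.1. The identification is by elimination.

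**2. The passages side by side.**

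| Source | Timing of the Sentio 1 SSQ12 |
|---|---|
| 8.2, objective C | not before one month of use |
| 9.4 flow chart; 9.5.4.1 | at Visit 2 |
| 9.1 | during the field trial |
| 9.4.1.1 | issued at fitting, to be completed before Visit 2 |
| 9.4.1.2 | returned at Visit 2, completeness check only |
| 12, Missing data | completed at the visit only if forgotten or not yet done |

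The first two rows can be met together, because the Visit 2 window opens only forward from one month. The next three rows describe home completion, with no lower limit on the day. Section 12 describes paper forms marked with the Subject ID and mentions no completion date. The signing and dating of source copies by site staff at visits would not show when the subject answered.

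**3. Days of use at completion.** Taking a month as 30 days, Visit 2 falls between day 30 and day 30 + 28 = 58 (section 6.2) or day 30 + 30 = 60 (section 9.1). A form completed before Visit 2 can carry any exposure from day 0 up to that visit. If Visit 2 is on day 30, every form completed earlier, as instructed, reflects less than one month. If Visit 2 is later, home completion can meet the objective, but nothing requires it.

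**4. The plan's own SSQ12 figure.** Section 11.1 gives n = 11, a difference of 1, an SD of the difference of 0.9, two-sided 5% and 90% power.
- Normal approximation: n = (0.9 × (1.960 + 1.282) / 1)² = 8.51, so 9. Power at n = 11 is 95.8%.
- Paired t: n = 11, with 91.2% power.

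The stated figure reproduces and is not in dispute. It supplies the scale for step 5: standard error of the mean difference = 0.9 / √11 = 0.27 points.

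**5. Illustration only.** The documents give neither the share of early forms nor the effect of answering early. With assumed values,

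shift in mean C3 = share early × mean difference per early form.

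- 25% early, 0.3 points: 0.25 × 0.3 = 0.075 points, or 0.075 / 0.27 ≈ 0.3 standard errors.
- 50% early, 1.0 point: 0.50 × 1.0 = 0.5 points, or 0.5 / 0.27 ≈ 1.8 standard errors.

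The upper figure needs both upper assumptions at once, and the sign is unknown. The range shows only that the effect could lie anywhere from negligible to material against the 1-point difference in section 11.1.

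**The case against.** The strongest reply is that the plan must be read as a whole. Objective C, the flow chart and section 9.5.4.1 all point to one month or later, Visit 2 is never planned before one month, and the take-home instruction can be read as asking subjects to have the form ready for that visit. Section 6.2.1 also says openly that self-report is gathered both in and after the field periods, so the Visit 2 entries may simply mark when the form is collected. The subjects already use a processor on the I1 implant, which may limit adaptation effects.

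Much of this stands, and it rules out several stronger readings:

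- A reader might infer that a form filled in after a few days fully complies with the plan. It does not: it conflicts with objective C and sits badly with sections 9.4 and 9.5.4.1. The plan fails to exclude such a form; it does not endorse it.
- A reader might infer that early and late forms could never be told apart. The subject-facing instructions, the form layout, the eCRF fields and the separate analysis and data validation plans to which sections 11 and 12 refer are not shown. Any of them may contain a timing rule or a date. What can be said is that this plan mentions neither.
- A reader might infer that completion at home rather than on site itself biases the score. Nothing in the documents supports that.

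What the reply does not remove is the case of Visit 2 at one month. There, following the stated procedure means answering before the month is complete. Reading the Visit 2 entries as a collection point leaves that unchanged.

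**Conclusion.** The point holds as an inconsistency between objective and procedure. The plan permits Sentio 1 SSQ12 forms that reflect less than one month of use, and its procedure leads to them when Visit 2 falls at one month. It rests on two conditions: that the take-home form is the SSQ12, and that no unseen instruction adds a timing rule.

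C1 and C3 may therefore combine early and adapted ratings. Direction and size cannot be determined from the documents; the 0.075 to 0.5 points above is assumption throughout. It would be wrong to infer that the trial's conclusion is at risk. The only stated success criterion (section 8.1.1) is functional gain, measured at Visit 2, and no decision rule depends on SSQ12. The correction is worth making because it is nearly free and lets the result answer objective C as written.

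**What to change.** Reconcile sections 9.1 and 9.4.1.1 with sections 8.2, 9.4 and 9.5.4.1. State that the Sentio 1 SSQ12 is completed at Visit 2, before any adjustment of the processor. The order needs stating because section 9.4.1.2 calls its sequence only a suggestion. Section 12 already allows on-site completion as a fallback, so this makes the fallback the rule.

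If home completion is kept: instruct subjects to complete the form no earlier than one month after fitting, record the completion date in the eCRF, and repeat any earlier-dated form at Visit 2.

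The cost is a sentence in each of two sections, a date field if forms still go home, and a few minutes for 12 items in a visit of 2-3 hours.

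On the planned dates, Visit 2 may already be over: a start on 15 November 2022 plus 8 weeks of enrollment gives 10 January 2023, and 60 further days gives about 11 March 2023, before Revision 4 of 4 July 2023. In that case, report whatever completion dates the paper forms carry, say how many forms predate one month or cannot be dated, and state the limitation when concluding on objective C.

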##### 9.4.1.2 Visit 2 follow up (1 month)

Following procedures will be carried out at visit 2. The flow below is a suggested flow, based on convenience for subject and investigator the order may be changed.

- AEs are assessed.
- Questionnaires is handed in and checked for completeness.
- Aided and unaided sound field thresholds are performed.
- Preference questionnaire is filled out.
- Adjustment of the Sentio 1 is considered.
  - Strength of retention magnet is considered and potentially changed according to the subject's needs and preference.
  - Finetuning is considered and Sentio 1 is adjusted according to the subject's needs and preference.

##### 9.4.1.3 Visit 3 follow up (1 year)

Following procedures will be carried out at visit 3. The flow below is a suggested flow, based on convenience for subject and investigator the order may be changed. Based on subject needs and preference the visit might be a remote visit.

- AEs are assessed.
- Adjustment of the Sentio 1 is considered

oticon MEDICAL	Title Clinical Investigation Plan BC114	Document no Doc-00117705	Revision 4	Page 22(39)
--------------------------	---	------------------------------------	----------------------	-----------------------

- Strength of retention magnet is considered and potentially changed according to the subject's needs and preference.
- Finetuning is considered and Sentio 1 is adjusted according to the subject's needs and preference.

#### 9.4.1.4 Visit 4 follow up (2 years)

Following procedures will be carried out at visit 4. The flow below is a suggested flow, based on convenience for subject and investigator the order may be changed.

- AEs are assessed.
- Change and adjustment of the Sentio 1 as applicable
  - Strength of retention magnet is considered and potentially changed according to the subject's needs and preference.
  - Finetuning is considered and Sentio 1 is adjusted according to the subject's needs and preference.
- Study termination

#### 9.4.1.5 Unscheduled visit(s)

If need for extra adjustment of the Sentio 1 or if other aspects arise that requires the attention of the investigator the subject's will be booked for an extra appointment.

### 9.5 Clinical Investigation Procedures

#### 9.5.1 Fitting and adjustment of Sentio 1

The fitting of the Sentio will follow clinical practice for bone anchored devices and will be made following the fitting procedure described in the Audiological manual [D].

The fitting procedure includes measurement of feedback limit and BC In-situ threshold for the frequencies 250, 500, 750, 1000, 1500, 2000, 3000, 4000, 6000 and 8000 Hz. If needed, the sound in Sentio 1 can be finetuned according to the patient's needs and preference. Also, the retention and comfort in relation to the magnet connection between the Sentio 1 and implant will be assessed, and if needed the magnet in the sound processor will be exchanged to a weaker or stronger magnet. At follow up visits further adjustment regarding finetuning and magnet retention is assessed.

#### 9.5.2 Clinical assessments

##### 9.5.2.1 Demographic Data and Baseline Measurements

Following subject characteristics will be collected upon enrollment:

- Gender
- Age
- Indication (MHL/CHL/SSD)
- Implanted side (L/R)
- Type of hearing loss on the non-implanted side (MHL/CHL, SSD, normal hearing, sensorineural hearing loss)
- Hearing solution on the non-implanted side (BAHS, conventional hearing aid, no hearing solution, other)
- Usage hours with current device

### 9.5.3 Performance Assessments

#### 9.5.3.1 Audiometry

Conventional pure tone audiometry (air-conduction and bone conduction). Tested frequencies for air-conduction are: 250, 500, 1000, 2000, 3000, 4000, 6000, 8000 Hz. Tested frequencies for bone-conduction are: 500, 1000, 2000, 3000, 4000 Hz. Masking is applied as per clinical practice and standard audiometry equipment is used (air-conduction is measured via insert phone or headphones (TDH39), bone conduction via e.g. B71).

If audiogram less than 3 years old can be retrieved from patient files and subject have not experienced any change in his or her hearing this can be used and full audiogram according to above does not need to be performed. Regardless of prior audiometry, the unmasked BC for the fitted side will be measured for all subjects.

#### 9.5.3.2 Sound field thresholds

Detection of thresholds for warble tones presented in sound field from loudspeaker placed at 1-meter distance, 0 degrees azimuth from the subject. Warble tones according to local clinical practice for sound field measurements at 250, 500, 1000, 2000, 3000, 4000, 6000, 8000 Hz are presented. All subjects have the non-operated ear blocked (but not masked).

Conditions	Directionality settings	Noise reduction	Feedback management system	Estimated time [min]
Sentio 1	Omni	Off	feedback management as prescribed	10
Unaided	/	/	/	10

#### 9.5.3.2.1 Functional gain

The functional gain is a calculation and uses the sound field thresholds as described above. Functional gain is defined as the difference between unaided and aided thresholds. In this investigation, functional gain is calculated for frequencies 250, 500, 1000, 2000, 3000, 4000, 6000, 8000 Hz. The average functional gain (PTA4) is calculated as the average of frequencies 500, 1000, 2000 and 4000 Hz.

